Appendix E – Flyer for Text Message Instructions

Instructions for Text Messages

You will be getting text message reminders to take your blood pressure (BP).

To make sure you are able to receive and send messages:

- 1 When you get the text from REACH OUT to take your BP, follow the instruction sheet for taking your BP at home
- 2 Text your BP to "REACH OUT" as xxx/xxx (for example: 135/80)

If you want to know all the changes you can make to your text messages, just text 'HELP'

You can take a break from getting text messages. Just text 'SNOOZE'

- After a 2-week break, you will start getting text messages again.

You can change how often you get text messages to remind you to take your BP.

- Text 'DAILY' to get text message reminders every day.
- Text 'WEEKLY' to get text message reminders once a week.

If you would like us to send a graph that tracks your BP readings, text 'GRAPH'

You can stop participating in the REACH OUT project at any time. Just text 'END'

Things to know before you decide to 'END':

- You won't receive any more text message reminders to take your blood pressure.
- We'll only contact you for follow-up at 6 months and 12 months.

Important: The text messages are not read by medical providers, so never text medical questions. If you are having an emergency, please call 911

Abbreviations we may use:
BP = Blood Pressure
ED = Emergency Department
Dr = Doctor
Meds = medications

REACH OUT
For Lower Blood Pressure

Have questions about REACH OUT study? Call or text the REACH OUT staff at [contact]

Appendix F – Reach Out Feedback

Name: _____

Date: _____

We took your blood pressure today as a part of your participation in the REACH OUT project.

Your blood pressure was: _____ / _____.

What does your blood pressure mean?

Blood Pressure Categories			
120 80 or lower	121 – 129 80 or lower	130 – 179 80 – 119	Above 180 120
Normal Blood Pressure	Borderline Blood Pressure	High Blood Pressure	Hypertensive Emergency
Awesome! Keep up the good work!	Talk to your doctor about your BP at your next appointment. Consider eating less salt, more fruits/veggies and exercising more to lower your BP.	See your Dr about your BP within the next month. You may need to start or change medications to help lower your BP. Consider eating less salt, more fruits/veggies and exercising more to lower your BP.	You need to call your Dr right away! You likely need to start, change or take more of your BP medications If you have you have symptoms such as chest pain, weakness, difficulty talking or confusion call 911

[figure not shown]
[figure not shown]
[figure not shown]
Some things I can do to manage my blood pressure better/Goals I can set for managing my BP:

[figure not shown]
[figure not shown]
[figure not shown]
[figure not shown]
- 1) _____
- 2) _____
- 3) _____

[figure not shown]
[figure not shown]
[figure not shown]
If you have questions about your blood pressure you should talk to your doctor. Your doctor will be able to answer your questions and set up blood pressure goals and treatments that are right for you.

If you have REACH OUT study questions, contact [contact].

Appendix I- Holiday Card Study Within A Trial

Introduction and Background

Holiday cards are frequently sent to research participants, yet the impact of this practice is not clear. The intended result is to maximize retention and maximize the amount of follow up data collected from participants on protocols. The trials group at the University of York, UK has organized the Christmas Card study within a trial (SWAT). [name] is the lead investigator. This SWAT has been registered as "SWAT 82: Sending Christmas cards to trial participants to improve retention – studies within trials (SWATs)" and has the Prometheus reference MR/R013748/1/SWAT 82 and was approved by the Yorkshire & The Humber – Leeds West Research Committee under project ID 27054.

Within the main protocol of REACH-OUT, sending retention materials is allowable. We propose to use this SWAT methodology to send holiday cards (Appendix J) to a random sample of participants currently active on the REACH-OUT protocol.

No data with protected health information or personal identifiers will be transferred outside of the REACH-OUT. Aggregate response rates per arm of the SWAT will be shared to the organizers of the SWAT in York.

Design

Inclusion:

The launch date is pending approval of this amendment, but we anticipate sending the cards in Winter 2020. All subjects currently active on the REACH-OUT protocol are eligible.

Exclusion:

Participants who have withdrawn from follow up visits.

Intervention:

We will create a randomization list of the current REACH-OUT participants, stratified by randomization group assignment (groups 1-8 will each have 1:1 randomization to holiday card versus no holiday card). In addition, within each of the 8 treatment groups, we will further stratify randomization of the holiday card by gender and age (<65 versus >65). Cards will be mailed.

Analysis – From SWAT:

The primary endpoint is retention – defined attendance at the next follow up visit. The secondary endpoints are cost per participant retained and response rate.

Subgroups will be identified for reporting, including those with an appointment within 30 days of expected delivery of the card, those who have 1st or 2nd visit next, and those who did not return the previous 4-week survey.

We will report proportions and differences in proportions with 95% confidence intervals for the primary endpoint and repeat this for all subgroups, including gender and age.

Analysis – Additional Specific to REACH-OUT

We will estimate additional subgroups using the defined stratification variables of REACH-OUT

The REACH-OUT specific primary endpoint is text-messaging engagement. This is a count variable, which for the 4 weeks prior to and after the expected card delivery is defined as the number of blood pressures reported by text over the number of blood pressures that were requested. Participants near the beginning (less than 4 weeks in) or end (less than 4 weeks from final visit) of REACH-OUT will be excluded from this analysis.

The main analysis of this will be using repeated measures binary logistic regression with a random effect. Each participant will have a line of data for each eligible blood pressure request. We will include an indicator variable for REACH-OUT assigned frequency of texts (weekly versus every other day) and SWAT group assignment (will be one in participants who were sent a card, for the eligible BPs that occurred after estimated receipt of card, and will be zero in all participants not randomized to card, and will be zero for all pre-delivery texts in the group randomized to card.) A random intercept for individual will be included. In addition, we will add a variable to account for the number of weeks before or after the estimated delivery of the card. Depending on model fit and number of observed outcome events, we will add in adjustment for the other two main REACH-OUT interventions (healthy behavior texts versus none, PCP facilitated transportation versus none), along with the gender, age, and pre-existing hypertension medications baseline stratification variables from the main REACH-OUT study.

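### The holiday-card retention analysis ignores the strata used to randomise the card, so its confidence interval is valid but slightly wider than the design earns

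*Protocol*

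**What the plan says.** Everything on this point is in Protocol Appendix I; the SAP does not mention the card study.

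- **Randomisation.** The list of current participants is "stratified by randomization group assignment (groups 1-8 will each have 1:1 randomization to holiday card versus no holiday card"), and "within each of the 8 treatment groups, we will further stratify randomization of the holiday card by gender and age".
- **Retention endpoint.** "The primary endpoint is retention – defined attendance at the next follow up visit". It is binary.
- **Retention analysis.** "We will report proportions and differences in proportions with 95% confidence intervals for the primary endpoint". The plan is then to "repeat this for all subgroups, including gender and age", and later "We will estimate additional subgroups using the defined stratification variables of REACH-OUT". No stratified or covariate-adjusted estimator is named.
- **Texting model.** This is a repeated-measures logistic regression with one row per blood pressure request. It always contains assigned text frequency, the card indicator, the week relative to delivery and a random intercept per participant. Other terms are conditional: "Depending on model fit and number of observed outcome events, we will add in adjustment for the other two main REACH-OUT interventions". The same condition governs gender, age and prior antihypertensive use. Appendix I gives no criterion for fit and no event threshold.

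**The concern.** When allocation is balanced within strata that predict the outcome, differences between strata cannot contribute to the card-versus-no-card contrast. The usual standard error of a difference in proportions does not know this and still includes the between-stratum variance. The reported interval is then wider than the actual uncertainty. Repeating the estimate within gender and age subgroups does not correct the overall interval.

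Any effect of a card on attendance is likely to be small, so there is no reason to report more uncertainty than the design leaves. Appendix I also departs, without giving a reason, from the practice in SAP sections 2.4 and 2.7. There the stratification variables enter the primary model unconditionally, and the exploratory endpoints are adjusted for age, sex, antihypertensive use and race.

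The texting model raises a separate and smaller issue. Part of the covariate list for its main analysis stays open until the data have been seen.

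**Working it through.** Appendix I states no sample size, power, effect size or interval width, so there is no figure to reproduce. N, attendance and prognostic strength below are assumptions.

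**Inputs**
- Strata: 8 arms x 2 genders x 2 age groups = 32 (Appendix I).
- N: 400 for illustration, range 200 to 480. The anchor is the roughly 400 randomised when the sample size was revised (Protocol 9.3). The mean stratum size is 400/32 = 12.5.
- Attendance p: 50% for illustration, range 30% to 50%. The anchor is the planned 50% loss to follow-up (Protocol 9.3).

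**Closed form.** The crude 95% half-width is 1.96 x sqrt(4p(1-p)/N). At N = 400 and p = 0.5 this is 1.96 x 0.05 = 9.80 percentage points. If the strata explain a share R2 of the variance in attendance, the adjusted half-width is the crude one times sqrt(1 - R2):
- R2 = 2%: 9.70
- R2 = 5%: 9.55
- R2 = 10%: 9.30
- R2 = 20%: 8.77

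Over the full ranges of N and p, the crude half-width runs from 8.2 to 13.9 points, with the same relative gains.

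**Simulation.** There were 4,000 replicates per row, with N = 400, 50% attendance, no card effect and 1:1 allocation within the 32 strata. Gender was assumed to split 60/40, and 15% were assumed to be in the older group. The crude difference was compared with a linear model containing the three arm factors, gender and age, with robust standard errors.

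| R2 | Crude SE | Adjusted SE | Ratio | True SD, crude | True SD, adjusted | Type I error, crude | Type I error, adjusted |
|---|---|---|---|---|---|---|---|
| 0% | 0.0499 | 0.0500 | 1.00 | 0.0497 | 0.0498 | 4.95% | 4.97% |
| 1.5% | 0.0498 | 0.0495 | 1.006 | 0.0486 | 0.0486 | 4.55% | 4.80% |
| 4.1% | 0.0496 | 0.0487 | 1.018 | 0.0482 | 0.0482 | 4.65% | 4.93% |
| 8.4% | 0.0492 | 0.0472 | 1.042 | 0.0473 | 0.0472 | 4.03% | 4.97% |
| 13.4% | 0.0488 | 0.0456 | 1.070 | 0.0460 | 0.0457 | 3.90% | 5.33% |

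The Monte Carlo error of a 5% rate is sqrt(0.05 x 0.95/4000) = 0.34 points. Only the last two crude rates are clearly below 5%.

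The true spreads of the two estimators are almost equal, so what adjustment corrects is the reported standard error.

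The bottom row needs strong predictors. The log-odds gaps were 0.6 for each arm factor, 0.8 for gender and 1.6 for age, divided by their SD, sqrt(3 x 0.3^2 + 0.4^2 + 0.8^2) = 1.034. That gives odds ratios of about 1.8, 2.2 and 4.7. The 1.5% row uses 0.3 times those gaps, giving odds ratios of about 1.2, 1.3 and 1.6.

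**Texting model.** Suppose 200 participants receive daily and 200 weekly requests over eight weeks. The rows number 200 x 56 + 200 x 8 = 12,800. At the church pilot's 47% response (Protocol 2.2.1) that is about 6,000 replies. With requests every other day, as Appendix I words it, the rows are 200 x 28 + 200 x 8 = 7,200, with about 3,400 replies. Both counts are before the exclusion of participants within four weeks of start or end. For person-level covariates the number of people matters more than the number of rows, but 400 people is still ample for five binary terms.

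**The case against.** The strongest case on the other side has four parts.

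1. **The crude interval is legitimate.** This stands. An unadjusted risk difference is a valid estimator, and its interval errs on the safe side. A reader might infer that the interval is wrong or that the estimate loses precision. Neither holds: true spread is 0.0460 against 0.0457 even in the strongest case.

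2. **The retention analysis is inherited.** Appendix I takes it from a registered multi-trial SWAT whose own protocol is not in these documents. That explains why crude results should still be supplied. It does not stop this trial from adding an adjusted estimate.

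3. **The texting model is less open than it looks.** This stands for the most part. A reader might infer that all the strata enter only conditionally. In fact assigned text frequency, one of the three factors that define the arms, is always included. The reference to event count reads as a sparse-data safeguard. A reader might also infer that several card odds ratios are on offer, because a logistic odds ratio shifts with covariates. Here the card indicator switches on after delivery and each person has a random intercept, so the contrast is largely within person. A small simulation (45 replicates per setting, N = 400, random-intercept SD 1.5, card log odds ratio 0.2, all assumed) moved the card log odds ratio by 0.001 on average and at most 0.03 when the five covariates were added, against a standard error of about 0.09.

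4. **Which visit is next is not a card stratum.** This stands. It is a named subgroup, and precision gained by adjusting for it is not a cost of ignoring the strata.

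**Conclusion.** The point holds in a limited form. The retention interval takes no account of the factors on which the card is stratified. At about 400 participants and 50% attendance, the crude standard error exceeds the adjusted one by roughly 1% to 7% over the assumed prognostic strengths, and by nothing if the strata do not predict attendance. The upper end requires large stratum effects. Coverage is at or slightly above nominal.

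A reader might infer that the retention analysis is chosen from the data; it is not, because its method is fixed in advance. Only the texting model has an open covariate list. That is a minor gap in pre-specification with little room to alter the card estimate.

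This is an improvement worth making in an ancillary study. It has no bearing on the blood pressure results.

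**What to change.** **Retention.** In Appendix I, make the main estimate a card-versus-no-card risk difference adjusted for main effects of the three intervention components, gender and age group. Identity-link regression with robust standard errors, or a standardised logistic model, would serve. Main effects are enough; 32 cells of about 12 people are too sparse to fit separately. Which visit is next may be added as an optional further covariate. Continue to report crude counts per card arm to the SWAT organisers.

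**Texting model.** Replace the conditional clause with a fixed list: the other two components, gender, age group and antihypertensive use, beside the terms already always included. State what will be done if the model does not converge.

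**Coding.** A fixed list needs settled definitions. The card strata are written as "we will further stratify randomization of the holiday card by gender and age (<65 versus >65"), which leaves age 65 unassigned. Appendix I also describes the higher text frequency as every other day, where the rest of the protocol and the SAP say daily. These passages must be reconciled.

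The cost is a few sentences in Appendix I and a few lines of code, using variables already collected. If the analysis has already been run, report the crude and fully adjusted results together.

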2.2.1 Reach Out-Flint Churches (HUM00082454)

Using a community-based participatory research (CBPR) approach, several mobile health components were developed including prompted BP self-monitoring, healthy behavior text messages,

and a text messaging roadmap. We then tested healthy behavior text messages and weekly prompted BP self-monitoring in three African American churches for 6 months. All text messages were delivered automatically through a text messaging platform developed by Mosio, who is also the vendor for this application.⁵³ A total of 48 participants received the intervention with a mean age of 58 (sd=9.8) years, all of whom were African American. Notably, 15% of the participants did not have a primary care provider. Participants responded to BP prompts 587 (47%) of the available 1248 person-weeks. All (100%) participants reported satisfaction with the Reach Out intervention. Overwhelmingly, participants did not want the mobile health intervention supplemented with phone calls, workshops, cooking demonstrations or internet modules.

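### The holiday-card texting model has no post-delivery term common to both arms, so a shared step or dip after delivery is partly credited to the card unless week is fitted as categories.

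*Protocol*

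**What the plan says.** The point concerns Appendix I of the protocol (Holiday Card Study Within A Trial), in the part headed as additional analysis specific to REACH-OUT. The endpoint is texting engagement, replies received out of replies requested, "for the 4 weeks prior to and after the expected card delivery". Cards are randomised within each trial arm: "groups 1-8 will each have 1:1 randomization to holiday card versus no holiday card". On timing, launch awaits approval of the amendment, and "we anticipate sending the cards in Winter 2020".

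Each participant has one row per BP request. "The main analysis of this will be using repeated measures binary logistic regression with a random effect", and "A random intercept for individual will be included". The fixed terms are:

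- the assigned texting frequency;
- a card variable, which is one for requests after estimated receipt in participants sent a card and otherwise "will be zero in all participants not randomized to card, and will be zero for all pre-delivery texts in the group randomized to card";
- a time variable: "we will add a variable to account for the number of weeks before or after the estimated delivery of the card".

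The other two trial interventions and the baseline stratification variables may be added if model fit and event numbers allow. None of these is a time term. The list contains no before/after indicator that applies to both card groups, and the appendix does not say whether week is linear, categorical or unsigned.

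**The concern.** The card variable is the product of card assignment and the post-delivery period. Without a post-delivery main effect, its coefficient draws on two comparisons: card versus no card after delivery, which is randomised, and after versus before within the card group, which is not. The no-card group helps remove a shared change over time only to the extent that the week variable can represent the shape of that change. A straight line cannot represent a step or a dip followed by recovery.

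The cut-point is the arrival of a holiday card in winter, so a shift in reply behaviour in both groups at about that time is plausible. A shared fall would make an inert card look harmful, and a shared rise would make it look helpful. The sub-study has a concurrent randomised control group that could remove such a shift completely.

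**Working it through.** **Inputs from the documents.** 1:1 allocation, a window of 4 weeks each side, a random intercept, and the card coding above (all Appendix I). The baseline reply rate in the simulations is 47%, from the churches pilot (Protocol 2.2.1): "Participants responded to BP prompts 587 (47%) of the available 1248 person-weeks".

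**Assumptions.** The documents give no sample size, effect or power for this sub-study, so there is no stated figure to reproduce. The following are assumed:

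- 400 participants for false-positive rates, half prompted weekly and half daily. Appendix I describes the high-frequency group as prompted every other day and the protocol body as daily; these passages need reconciling.
- Random-intercept SD of 0.5 or 1.5 logits.
- A shared change of −0.5 logit and a true card effect of zero.

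**1. Closed form for a shared step, linear week (within-person approximation).** Let T be centred week, P the centred post-delivery indicator (variance 1/4), and d the step shared by both groups. With half the sample sent a card, the normal equations for the week slope b and card coefficient c are

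- var(T)·b + ½cov(T,P)·c = d·cov(T,P)
- ½cov(T,P)·b + ⅛·c = d/8

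so c/d = (1 − r²)/(1 − r²/2), where r² is the squared correlation of T and P.

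| Week coding | r² | Share of step credited to card |
|---|---|---|
| −4..−1, 1..4 | 0.833 | 0.167/0.583 = 29% |
| −4..3 (same as −3.5..3.5) | 0.762 | 0.238/0.619 = 38% |
| continuous | 0.750 | 0.250/0.625 = 40% |

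**2. Allowing for the random intercept.** Generalised least squares with compound symmetry and weeks −3.5 to 3.5 gives 27%, 33%, 35%, 38% and 38% at within-person correlations of 0.1, 0.3, 0.5, 0.8 and 0.95. With weeks −4..−1, 1..4 the range is 20% to 28%.

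**3. What does not leak under linear week.** If the shared change is kT, then b = k and c = 0. If it is a dip of one week each side of delivery, its covariances with T and P are both zero, so c = 0.

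**4. Simulated random-intercept logistic models.** Share of the shared −0.5 logit change credited to the card:

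| Shared change | SD | Linear week | Categorical week |
|---|---|---|---|
| Linear drift | 0.5 | −1% | 0% |
| Step at delivery | 0.5 | 21% | −1% |
| Two-week dip after delivery | 0.5 | 34% | 2% |
| Change over weeks −1 to +2 | 0.5 | 13% | 2% |
| Step at delivery | 1.5 | 28% | 3% |
| Step, weeks coded −4..3 | 1.5 | 38% | not run |

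Weeks are coded −4..−1, 1..4 except in the last row. At SD 0.5, linear week plus a common post-delivery indicator gave the same shares as categorical week. Unsigned weeks did worst: 23% to 88% across the four shapes, and 55% for a plain linear drift.

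**5. On the odds-ratio scale.** Suppose replies fall from 50% to 40% in both groups (logit −0.405) as a step at delivery, and the card does nothing. At 20% leakage the card odds ratio is exp(−0.081) = 0.92; at 40% it is exp(−0.162) = 0.85.

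**6. False positives at nominal 5%.** These use 400 participants, SD 1.5, a shared step of −0.5 logit and linear week. The inert card was declared significant in about 45% of 62 datasets (weeks −4..−1, 1..4) and 74% of 70 datasets (weeks −4..3). With no shared change the figure was about 5% (75 datasets). With the step and categorical week it was 2% (45 datasets). The empirical standard error was used, and the replicates are few: √(0.45 × 0.55/62) = 0.06, so the first figure carries a Monte Carlo error of about 6 percentage points.

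**7. Price of the fix.** In the within-person limit, the variance of the card term left after a linear week is ⅛(1 − r²/2), which is 0.0729 at r² = 0.833 and 0.0781 at r² = 0.75. After a common post-delivery term it is 1/16 = 0.0625. The standard error therefore rises by a factor of √(0.0729/0.0625) = 1.08 to √(0.0781/0.0625) = 1.12.

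**The case against.** The strongest reply is that the plan already has a time term applying to both groups and spanning the post-delivery period, and never says it is linear. Fitted as categories, it removes every shared week-level change, and the card coefficient is then sound. This stands as far as it goes: the text does not exclude the safe coding. It does not secure it either. One variable for a number of weeks reads most naturally as one numeric term, and an unsigned reading would be worse.

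A reader might infer that any seasonal change in texting biases the card effect. The documents do not support that: even with linear week, a steady drift and a dip symmetric about delivery leave the card coefficient at zero, and a change straddling delivery leaks only modestly. Nor can a reader conclude that the analysis will have an inflated error rate. No size, shape or timing of a seasonal shift is given, and delivery is placed only in winter, with the launch date still open.

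It is also fair to say that omitting a card-group main effect is no error. Cards are randomised, so equal pre-delivery means are a legitimate constraint. Only the handling of common time needs to change.

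**Conclusion.** The concern holds conditionally. The card variable is entered without a post-delivery term common to both groups, and the only common time control has unstated coding. Under the most natural reading, one linear week term, roughly 20% to 40% of a shared step at delivery is credited to the card, depending on week coding and within-person correlation. A shared post-delivery dip also leaks. In the closed form, the fraction does not depend on the size of the step; the resulting error rate does, and also depends on sample size, between-person variation and timing, all assumed here. The false-positive figures show what could happen and are not predictions.

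The consequence is small for the trial. Only the added texting-engagement analysis is affected. The sub-study's retention endpoint is a difference in proportions between randomised groups, and the trial's systolic BP analysis does not use this model.

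**What to change.** State the coding of week and let common time be flexible. Either of these is enough:

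- enter week from delivery as categories, which is closest to the existing text; or
- keep week as a signed linear term and add a post-delivery indicator for all participants.

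In both cases read the card effect from the existing card-by-post variable, and keep the random intercept and assigned-frequency term. A card-group main effect may be added but is optional.

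An alternative is to compare post-delivery replies between the randomised groups, adjusting for each participant's pre-delivery reply rate.

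The cost is one extra term for the indicator, or a few for categories, and no new data. The interval for the card effect widens by about 8% to 12% in the within-person limit; in the simulations at 400 participants with no shared change, the standard errors were almost the same (0.081 linear, 0.080 categorical).

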6 STUDY INTERVENTIONS

6.1 Intervention and strategy components

As stated, Reach Out tests three intervention components: 1) healthy behavior text messaging (daily vs. none); 2) prompted BP self-monitoring (daily vs. weekly); 3) facilitated primary care provider scheduling and transportation (yes vs. no). Participants will be randomized into one of eight arms (Table 2) for the 12-month intervention. For example, in arm 1, the participants will not receive healthy behavior based texts. They will receive weekly prompted BP self-monitoring. Arm 1 is the lowest intensity group (weekly prompted self-monitoring and reporting of BP) and will serve as the effective control group. There is no "untreated" control group given the efficacy of prompted blood pressure self-monitoring and feedback from the community following the preliminary studies. In all of these intervention groups, throughout the duration of the study, if a participant seems to be consistently unresponsive or responding in error, we may attempt to

Arm	Healthy Behavior Text	Prompted BP self-monitoring frequency	Facilitated Primary Care appointment scheduling and transportation
1	No	Low	No
2	Yes	Low	No
3	No	High	No
4	Yes	High	No
5	No	Low	Yes
6	Yes	Low	Yes
7	No	High	Yes
8	Yes	High	Yes

contact them via phone, text message, or their preferred means, to ensure they are not in need of technology or study assistance.

Additionally, if any requests are sent in by the participant to modulate, pause, or stop any of their intervention components, we will give the participant the option if they may still be contacted for outcome assessments or appropriate other intervention components, if possible. Certain intervention components deemed not possible because of coronavirus or institutional guidance, may not be able to be implemented.

Figure 1 Reach Out Study Design and Incentives (within the randomization table, - boxes indicate low intensity, + boxes indicate high intensity)

6.1.1 **Text messages**

Text message frequency will be dependent on the randomization of the participant. Participants randomized to receive healthy behavior text messages will receive them daily.

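### The holiday-card texting model has only a random intercept, so its standard error for the card effect is too small if participants' texting rates change differently over the eight weeks

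*Protocol*

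**What the plan says.** The Protocol's Appendix I, under the analysis specific to REACH-OUT, makes texting engagement the primary endpoint of that part of the card sub-study. It is the share of requested blood pressures that were texted, "for the 4 weeks prior to and after the expected card delivery". The planned model is as follows.

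- Type: "The main analysis of this will be using repeated measures binary logistic regression with a random effect".
- Unit: "Each participant will have a line of data for each eligible blood pressure request".
- Card term: 1 for requests after estimated receipt in the card group; it "will be zero for all pre-delivery texts in the group randomized to card", and is always 0 in the no-card group.
- Time: "we will add a variable to account for the number of weeks before or after the estimated delivery of the card".
- Within-person correlation: "A random intercept for individual will be included".

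No random slope, person-by-period effect, serial correlation or robust variance is named. Allocation is by participant: "groups 1-8 will each have 1:1 randomization to holiday card versus no holiday card". No alpha, sample size or power is given for this model.

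Two other places bear on the point. SAP section 2.5(a), for the longitudinal blood pressure model, specifies both a random intercept and a random slope over time. On prompt frequency, Appendix I describes the more intensive group as prompted every other day, whereas Protocol section 6.1.2 says daily.

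**The concern.** The card indicator is zero before delivery in both groups, so the card effect is estimated largely from how each person's response rate changes across delivery. Because the card is assigned to people, the proper yardstick is how much that change varies between people. A random intercept allows people to differ in level. Apart from the shared weeks term, it then treats each person's requests as independent. If some people fade, lapse or pick up for their own reasons, their post-delivery rows move together, and the model counts each row as fresh evidence about the card.

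The model's standard error would then be too small. Chance imbalance between the groups in who drifted could be reported as a card effect on texting.

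**Working it through.** **No planned figure to reproduce.** The documents state no error rate or power for this model. The check is a simulation with no card effect: fit the model as written and count two-sided Wald rejections at 0.05.

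**Inputs from the documents.** Four weeks before and four after; 1:1 card allocation; weekly prompts in one group and either every-other-day (Appendix I) or daily (section 6.1.2) in the other. Rows per person are 8 × 1 = 8 weekly, 8 × 3.5 = 28 every other day, 8 × 7 = 56 daily. The average response is near the 47% in the church pilot (section 2.2.1).

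**Assumed, because not given.** 300 participants, half per frequency; person-level SD 1.5 logit; alpha 0.05; all drift sizes.

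**Two forms of personal drift, on one scale.** Form A is a pre/post shift with a given SD. Form B is a personal linear slope per week. With weeks coded −4 to −1 and 1 to 4, the period means are −2.5 and +2.5, so the pre/post SD is 5 × the slope SD: slopes of 0.05, 0.1, 0.2 and 0.3 correspond to 0.25, 0.5, 1.0 and 1.5 logit. For scale, someone at 50% who moves up by 0.5 or 1.0 logit reaches 1/(1+e^−0.5) = 62% or 1/(1+e^−1) = 73%.

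**False-positive rate of the model as written** (nominal 5%)

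| Pre/post SD (logit) | Every other day, A (two runs) | Every other day, B | Daily, A | Daily, B |
|---|---|---|---|---|
| 0 | 4% | not run | 4.0% | 5.4% |
| 0.25 | 5%, 6.0% | not run | 7.0% | 6.2% |
| 0.5 | 7.5%, 8.5% | 7.4% | 10.3% | 10.1% |
| 1.0 | 13%, 15% | 13.9% | 23.0% | 24.1% |
| 1.5 | not run | 22.6% | not run | 34.5% |

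Form A used 400 data sets per scenario where the number is recorded (Monte Carlo SE about 1 to 2 points); form B used 800 (about 0.8 points at a 5% rate). Dividing by 5%, every-other-day prompts at SD 0.5 to 1.0 give 7.5/5 = 1.5 to 15/5 = 3 times nominal. Daily prompts give about 10/5 = 2 to 24.1/5 = 4.8 times. The extreme is 34.5/5 = 6.9 times. Two more daily form A runs gave 12.5% at SD 0.5 and about 30% at SD 1.0. The run behind the 30% also rejected 9% with no drift, so it reads high and is not relied on.

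**Check on the mechanism.** In form B the mean card estimate stayed within 0.01 logit of zero. At slope SD 0.2 with daily prompts, the model's SE was 0.086 against an actual SD of 0.145. The implied rejection is 2Φ(−1.96 × 0.086/0.145) = 2Φ(−1.162) = 24.5%, matching the simulated 24.1%. With every-other-day prompts, 2Φ(−1.96 × 0.113/0.152) = 14.5%, against 13.9%.

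**Other scenarios.**
- Autocorrelated weekly deviations (correlation 0.7), daily prompts: 11.0% at SD 0.5 and 19.9% at SD 1.0.
- A 2% weekly chance of stopping for good, equal in both groups: about 12% every other day, 18% daily.
- Slope SD 0.2, daily prompts: 24.1% at N=150; 22.0% with person-level SD 2.5; 27.3% in the high-frequency group alone; 7.4% in weekly participants alone.
- A common post-delivery term does not help: 24.3% at pre/post SD 1.0, daily.

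**Remedies on simulated null data.**
- Participant-clustered SEs on the planned model: 4.9% to 6.2% across all form B and autocorrelated scenarios, and 4% to 7% under form A.
- One record per person with robust SEs: 2.5% to 4.8%.
- Random slope for week (daily, slope SD 0.1, 0.2, 0.3): 5.9%, 6.1%, 5.9%.

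**The case against.** The strongest reply is that every inflation figure depends on a drift size that no document supplies. That stands. A reader might infer that this analysis will produce 2 to 5 times the nominal false positives. The documents do not support an unconditional multiple: with small drift the error rate is near nominal, and on Appendix I's own every-other-day wording it reaches about 3 times at a pre/post SD of 1.0 logit.

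Two other stronger readings also fail. One is that the model assumes no change in anyone's texting; in fact the weeks term absorbs change common to all, and only individual departures are left out. The other is that drift is mistaken for a card effect on average; because the card is randomised, drift widens the true sampling error without shifting the estimate.

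Section 6.1 might be cited as proof of drift, since staff may contact people "if a participant seems to be consistently unresponsive or responding in error". That passage concerns technical or study help. It says nothing about how much texting rates vary, and such contact would tend to shorten lapses; the permanent-stopping scenario ignores it.

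What survives is the structure. Nothing in the planned model lets individuals change differently, although participants can alter or snooze their own prompts (section 6.1.2 and Appendix E) and the SAP allows for individual trajectories in its longitudinal blood pressure model.

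**Conclusion.** The point holds as a fault in the error bars. If participants' texting rates change differently over the eight weeks, the planned model understates the standard error of the card effect and rejects a true null too often; the estimate stays unbiased. The multiples in the table are conditional on N=300, two-sided 0.05, half the participants at each frequency and the assumed drift. They cannot be narrowed until the two statements of prompt frequency are reconciled, since that choice changes the inflation materially.

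The issue is minor. It affects one endpoint of a nested sub-study. The sub-study's retention endpoint, analysed as differences in proportions, is untouched, as are the trial's systolic blood pressure and primary-care analyses.

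**What to change.** In Appendix I, keep the planned model but state that the confidence interval and p-value for the card effect will use participant-clustered (robust) standard errors. State the alpha for this test, and reconcile the prompt frequency with section 6.1.2.

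An alternative is one record per person: regress the post-delivery proportion of blood pressures texted on card assignment, pre-delivery proportion and assigned frequency, with robust standard errors. This changes the effect measure from a conditional odds ratio to a difference in proportions, so the choice should be made in advance.

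A random slope per individual is a further option if it converges. Weekly participants give only about four yes/no responses per period, and only a slope over weeks was tested here, not a random post-delivery change.

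The cost is one sentence in the appendix and a short change to the code, on the same data. The interval widens only as far as the drift requires. With no drift, the model SE already equals the true SD (both 0.088). At slope SD 0.2 with daily prompts, the half-width would go from 1.96 × 0.086 = 0.17 to about 1.96 × 0.145 = 0.28 logit.
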